IRB Minimal Risk Protocol Template

Note: If this study establishes a human specimen repository (biobank) for research purposes, do not use this template. Use the Mayo Clinic Human Specimen Repository Protocol Template found on the IRB home page under Forms and Procedures at http://intranet.mayo.edu/charlie/irb/

First-time Use: Use this template to describe your study for a new IRB submission.

- 1. Complete the questions that apply to your study.
- 2. Save an electronic copy of this protocol for future revisions.
- 3. When completing your IRBe application, you will be asked to upload this template to the protocol section.

Modification: To modify this template after your study has been approved:

- 1. Open your study in IRBe. Click on the study 'Documents' tab and select the most recent version of the protocol. Save it to your files.
- 2. Open the saved document and activate "Track Changes"..
- 3. Revise the protocol template to reflect the modification points , save the template to your files
- 4. Create an IRBe Modification for the study and upload the revised protocol template.

General Study Information

Principal Investigator: [name]., P.E.

Study Title: Comparative Effectiveness between Microprocessor Knees and Non-Microprocessor Knees

Protocol version number and date: Version 1.3, September 2014

Purpose

Hypothesis:

Hypothesis 1a: Differences exist between Microprocessor Knees and Non-Microprocessor Knees. Hypothesis 1b: Differences exist between the prosthetic and non-prosthetic limb for each prosthetic knee. Hypothesis 2: Differences exist in fall rates between amputees using Microprocessor Knees and Non-Microprocessor Knees.

Aims, purpose, or objectives:

This study will assess if the functional performance and musculoskeletal outcome of transfemoral amputees are improved after receiving a Microprocessor Knee (MPK) compared to a Non-Microprocessor Knees (NMPK).

Aim 1: Quantify the functional efficacy and satisfaction of transfemoral amputees wearing different prosthetic knee joints.

Aim 2: Assess the safety of transfemoral amputees wearing different prosthetic knee joints. Background (*Include relevant experience, gaps in current knowledge, preliminary data, etc.*):

MPKs are prosthetic knees that use a microprocessor to control the prosthetic knee mechanism and adjust knee stiffness. Comparative studies have documented improved gait symmetry (Kirker, *Clinical Rehabilitation*. 10:267-273, 1996; Schmalz, *Gait and Posture*. 16(3):255-263, 2002) and lower energy consumption (Schmalz, *Gait and Posture*. 16(3):255-263, 2002; Taylor, *Prosthetics and Orthotics International*. 20:116-121, 1996; Buckley, *Archives of Physical Medicine and Rehabilitation*. 78:330-330) when using a MPK. Multiple studies (Hafner, *Archives of Physical Medicine and Rehabilitation*. 88(2):207-217, 2007; Kahle, *Journal of Rehabilitation Research and Development*. 45(1):1-14, 2008; Highsmith, *Prosthetics and Orthotics International*. 34(4):362-377, 2010) have shown that MPKs are more effective at preventing falls than NMPKs. Blumentritt evaluated the safety of a MPK vs. NMPK in the gait laboratory and demonstrated that the MPK offered the highest degree of safety and was the most suitable prosthetic intervention for preventing falls (Blumentritt, *Journal of Prosthetics and Orthotics*. 21(1):2-15). Kaufman (Kaufman, *Gait and Posture*. 26:489-493, 2007) demonstrated significantly improved balance, a more normal gait, and significantly more reliance on the MPK prosthesis, and that amputees spontaneously increase their activity in the free-living environment when using MPKs. The users' subjective feedback was that the MPK improved their quality of life. This study seeks to gather additional experience of community-living, transfemoral amputees using MPKs.

Our previous and current research activities demonstrate our abilities to conduct this proposed research program and yield novel research findings. Of particular relevance to this study is our prior objective comparison of MPKs to NMPKs (Kaufman, Gait and Posture. 26:489-493, 2007; Kaufman, Archives of Physical Medicine and Rehabilitation. 87(7): 1382-1385, 2008). Additionally, we are currently able to quantify activity in the free-living environment using the Actigraph, a commercially available activity monitoring device. The monitor is able to measure 3D acceleration and record the data using on-board memory. The activity monitor has been used by this research team to record the activities-of-daily-living of a transfemoral amputee for four continuous days while using a MPK. These data revealed that a large portion of the day was spent performing low level activity. There was asymmetry between the prosthetic and sound limb with more activity on the sound side. Finally, we have the capability to measure variable cadence in the free-living environment and have used this capability to study patients before and after total hip replacement surgery. These data demonstrate our ability to measure activity level in the field over multiple continuous days and provide a meaningful interpretation, and are able to provide a unique perspective on the patient's prosthetic usage. Our laboratory has also been conducting multiple studies utilizing a biweekly fall tracking mailer to record number of falls and details surrounding these falls. We currently have more than 80 subject-years of fall tracking under these IRBs that demonstrate our ability to successfully monitor subject falls via biweekly mailings.

Subject Information - charts, records, images, or specimens are considered 'subjects'

Target accrual: Proposed number of subjects to be included in your study at your site. "Subjects" may include Mayo Clinic charts, records, or specimens, **and/or** charts, records, or specimens received at Mayo Clinic from external sources for collaborating analysis by the investigator under this IRB application: Target accrual is 50 subjects. 75 subjects may be screened to reach this target accrual.

Subject population: Subjects will include 50 unilateral transfemoral amputees, age 55 and over. No restrictions will be placed on gender or race. Efforts will be made to included equal numbers of subjects below and above 65 years of age.

Inclusion Criteria:

- Unilateral transfemoral amputee
- Medicare Functional Classification Level K2 or K3
- Currently using NMPK prosthesis
- Current NMPK prosthesis is well fitting at the socket
- No current stump problems, such as skin breakdown
- Able to ambulate without a gait aid

Exclusion Criteria:

- Previous neuromuscular complications currently affecting gait
- Currently undergoing dialysis treatments
- Amputation of the contralateral limb
- Poor fit of current NMPK prosthesis

Will a Certificate of Confidentiality be obtained? If yes, provide an explanation. No.

Study Design

Methods: Describe, in detail, the research activities that will be conducted under this protocol:

The study design is a reversal design whereby only the prosthetic knee joint will be changed. Each subject will be tested using their current NMPK, fit and tested with a MPK, and then tested again with their NMPK, e.g. A-B-A design. MPK prostheses from all manufacturers will be considered appropriate for testing. Each MPK to be used in this study is FDA approved. Each subject will be given an acclimation period (typically ~4 months) consistent with other similar studies (Hafner, *Archives of Physical Medicine and Rehabilitation*. 88(2):207-217, 2007; Kahle, *Journal of Rehabilitation Research and Development*. 45(1):1-14, 2008; Kaufman, *Archives of Physical Medicine and Rehabilitation Research and Development*. 45(1):1-14, 2008; Kaufman, *Archives of Physical Medicine and Rehabilitation Research and Development*. 46(3): 417-433, 2009) before testing is commenced on the MPK. The foot will be in the L5981 class, e.g. flex foot or equivalent. The same socket, suspension, and foot will be used throughout the study in order to eliminate these confounding variables. All prosthesis fittings will be performed by the subject's own certified prosthetist according to manufacturers' fitting guidelines.

Patient Function (Efficacy): Field based measurements will be obtained using ActiGraph activity monitors attached to waist, and bilaterally to the ankle and thigh for a period of 4 consecutive days, including 2 weekdays and 2 weekend days. The subject will don the monitors in the morning after waking and remove them prior to sleeping.

Patient Satisfaction and Safety: The subject's self-assessed satisfaction and safety during the previous four weeks in their free-living environment will be measured at the end of each prosthetic rotation. The general health SF-36 questionnaire and condition-specific Prosthesis Evaluation Questionnaire (PEQ) will be used to quantify patient satisfaction. The PEQ addendum (PEQ-A), 14 additional questions used to quantify subject confidence, concentration, stumbles, and falls will also be administered to the subjects. To account for falls preceding the 4 weeks covered by the SF36 and PEQ surveys, bi-weekly fall tracking mailers will be filled out

by subjects. Subjects will also fill out the Patient-Specific Functional Scale at each of the 3 evaluation points. This scale asks the subject initially what activities that are important to them are impossible or difficult to do with their current (NMPK) prosthesis. These activities and difficulty levels are revisited when using the MPK and again when switched back to the NMPK.

All study materials will go to subjects via mail and will be returned to study staff by postage paid envelopes.

Resources: Describe the available resources to conduct the research (personnel, time, facilities, mentor commitment, etc.):

All expenses (personnel, materials, postage) are covered by a research contract with the American Orthotic and Prosthetic Association (AOPA). Research activities will be carried out by the PI and Motion Analysis Laboratory staff listed on this IRB application. Costs associated with MPK prosthesis components and their fitting will be covered directly by AOPA.

Check all that apply. If none apply, leave blank:

This is a multisite study involving Mayo Clinic and non-Mayo Clinic sites. When checked, describe the research procedures/activities being conducted **only** at Mayo Clinic:

Mayo Clinic staff will be engaged in research activity at a non-Mayo Clinic site. *When checked, provide the location and a detailed description of the Mayo Clinic research staff involvement.*

This study is to establish and/or maintain an ongoing database or registry for research purposes only.

The research involves contact or interaction with subjects, for example, surveys, questionnaires, observation, blood draw.

The study involves audiotaping or videotaping

Review of Chart, Images, Specimens

Provide the date range for collection of data and/or specimens that will be included in your research dataset. (*Example: 01/01/2000 to 12/31/2012*)

Date range: From __/_/ to __/_/___

Check all that apply:

This study involves only data and/or specimens that exist at the time this application is submitted to the IRB (IRB submission date). No data or specimens will be collected beyond this date.

This study involves only data and/or specimens that will be collected after submission to the IRB.

The study involves data and/or specimens that exist at the time of submission to the IRB **and** data and/or specimens that will be collected after submission to the IRB, for example a study that includes collection of existing data and prospective collection of specimens.

Data and/or specimens used in this study are collected under another IRB protocol. *When checked, provide the IRB number(s) from which the research material will be obtained and check the box below to attest that subjects have provided consent for future use of their data and/or specimens, as described in this protocol.*

IRB Number(s):

□Subjects have provided consent for use of their data and/or specimens, as described in this protocol.

Other data sources will be utilized in this study. When checked, provide all data sources:

Data Confidentiality, HIPAA Subject Identifiers

Review the list of subject identifiers below and, if applicable, check the box next to each subject identifier being recorded at the time you are collecting/abstracting data/specimens for use in this study.

Subject Identifiers: Individually identifiable information, including demographic data, that identifies the individual or for which there is reasonable basis to believe it can be used to identify the individual. NOTE: Identifiers apply to subjects enrolled in your study and to the subject's relatives, household members, employers, etc.

Internal refers to subject identifiers that will be included in the dataset maintained by the study team. **External** refers to subject identifiers that will be shared with persons outside of the immediate study team, for example, sent to an external collaborator or shared with a national registry.

SUBJECT IDENTIFIERS Check all that apply	INTERNAL IDENTIFIER	EXTERNAL IDENTIFIER
Name	Х	
Social Security number		
Medical record/patient registration number, lab accession, specimen or	Х	
radiologic image number		
Study number, subject ID, or any other unique identifying number,	Х	
characteristic or code that can be used to link the identity of the subject to the		
data		
Dates: All elements of dates [month, day, and year] directly related to an	Х	
individual. Their birth date, date of death, date of diagnosis, etc.		
Note: Recording a year only is not a unique identifier.		
Medical device identifiers and serial numbers		
Biometric identifiers, including finger and voice prints, full face photographic		

images and any comparable images		
Web Universal Resource Locators (URLs), Internet Protocol (IP) address		
numbers, email address		
Street address, city, county, precinct, zip code, and their equivalent geocodes	Х	
Phone or fax numbers	Х	
Account, member, certificate or professional license numbers, health		
beneficiary numbers		
Vehicle identifiers and serial numbers, including license plate numbers		
If None of the above identifiers will be recorded or maintained in the	None	None
dataset and/or sent outside of the study team, please check "None".		

Statistical Information

Note: Power analyses and study endpoints are not needed for a pilot or feasibility studies.

No statistical information. *If checked, please explain*: Statistical Considerations

Power Statement: The study power is based on an effect-size approach (Cohen, *Psychological Bulletin*. 112:155-159, 1992). Based on a paired design with 50 subjects enrolled, there will be 80% power to detect differences in means between the two devices (MPK vs. NMPK) of at least 0.56 standard deviations, which is considered to be a medium effect size. This sample size is larger than previous MPK studies (Hafner, *Archives of Physical Medicine and Rehabilitation*. 88(2):207-217, 2007; Kahle, *Journal of Rehabilitation Research and Development*. 45(1):1-14, 2008; Kaufman, *Archives of Physical Medicine and Rehabilitation*. 87(7): 1382-1385, 2008), where the number of subjects ranged from 15 to 21.

Data Analysis Plan:

The purpose of this study is to compare the functional efficacy, patient satisfaction, and safety of two prosthesis designs: MPK vs. NMPK. The effects of these two prosthesis designs on these outcome variables will be evaluated using a one-factor repeated measures ANOVA. If the data are not sufficiently Gaussian, a non-parametric procedure such as Friedman's test will be used. Comparisons of A1 versus B, and A2 versus B will be also conducted using multiple comparison procedures or contrasts following the global ANOVA or Friedman's test. All procedures and analysis methods proposed in this study have been used previously and have been thoroughly validated.

The tri-axial accelerometer signals will be processed to yield activity levels of none, low, medium and high. Statistical analysis will determine if there are differences in activity level between the two prosthetic designs. Post-hoc analyses will be performed to determine which activity subscales differ between the prosthetic designs. Asymmetry between the prosthetic and non-prosthetic limb will be quantified using the asymmetry index described by Kaufman et al (Kaufman, *Journal of Pediatric Orthopedics*. 16(2):144-150, 1996). Variations in cadence will be quantified, since the data suggests that K2 patients benefit from a MPK (Theeven, *Journal of Rehabilitation Medicine*. 43(10):906-915, 2011; Burnfield, *Prosthetics and Orthotics International*. 36(1):95-104, 2012). Age related changes in gait will also be quantified.

The SF-36 will be used to determine if quality of life improves with a MPK. A multivariate approach will be used to compare all PEQ subscales simultaneously. If the overall test is significant, post-hoc analyses will be performed to determine which subscales differ between prosthetic designs. The PEQ-A will be grouped according to subject matter content (concentration, confidence, stumbles, falls) and tested to determine if there are differences due to prosthetic design. The information about falls from the biweekly fall tracking mailers will be compiled and compared across prosthesis type (MPK vs. NMPK). The Patient-Specific Functional Scale scores will be compared across time points as well.

Endpoints

Primary: Complete data collection of all subjects and complete statistical analyses Secondary: Manuscript publication

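### Apart from falls on the bi-weekly mailers, no MPK measurement is planned for a subject who stops the MPK before the post-acclimation test

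*Combined protocol and SAP*

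**What the plan says.** The design is A-B-A: own NMPK, then MPK, then NMPK again. Under Study Design, Methods: "Each subject will be given an acclimation period (typically ~4 months) consistent with other similar studies", and this comes "before testing is commenced on the MPK".

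Under Patient Satisfaction and Safety, self-assessed satisfaction and safety over the previous four weeks "will be measured at the end of each prosthetic rotation". This covers the SF-36, PEQ and PEQ-A. The Patient-Specific Functional Scale is completed at three evaluation points. Activity is monitored for four days as part of testing.

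Falls are handled differently: "To account for falls preceding the 4 weeks covered by the SF36 and PEQ surveys, bi-weekly fall tracking mailers will be filled out" by the subjects. The Data Analysis Plan compares these falls by prosthesis type.

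The named analyses are a one-factor repeated measures ANOVA or Friedman's test, with A1 versus B and A2 versus B contrasts. The documents contain no assessment for a subject who gives up the MPK early, no record of stop date or reason, no analysis set, no missing-data rule and no dropout allowance. The Endpoints section simply takes complete data on all subjects as the goal.

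**The concern.** To be measured on the MPK, a subject must remain on it for about four months. Loss of the B value can therefore be linked to how well the MPK works for that person, which sets it apart from ordinary missing data. The stated aim is whether outcomes improve after receiving an MPK, and that is a question about everyone fitted. If some subjects give the knee up early because it does not suit them, the results for activity, quality of life, satisfaction, confidence and stumbles describe those who stayed.

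The analysis is unlikely to repair this. Friedman's test and classical repeated measures ANOVA, in their standard forms, drop a subject without B. A mixed model keeps the A1 value, but that value says nothing direct about the subject's own B minus A1 difference. A measurement not taken at stopping cannot be obtained later.

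**Working it through.** **1. The plan's own figure.** For 50 paired subjects and 80% power, the Power Statement gives a detectable difference "of at least 0.56 standard deviations, which is considered to be a medium effect size". Alpha is not stated; I assume 0.05 two-sided. Then (1.960 + 0.842) × √(2/50) = 0.560, so 0.56 reproduces. This is the formula for two independent groups of 50, equivalent to a paired design with zero within-subject correlation. A paired t-test on the SD of the difference with 50 pairs detects 0.40. Either way, the figure requires all 50 subjects to supply both an A and a B value. The Target accrual entry, "Target accrual is 50 subjects. 75 subjects may be screened to reach this target accrual", is a screening allowance and leaves no margin for loss after enrolment.

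**2. Which outcomes are exposed.**

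| Outcome | Planned MPK measurement | Planned value if the MPK is stopped early |
|---|---|---|
| Activity monitors | after acclimation | none scheduled |
| SF-36, PEQ, PEQ-A | end of rotation, four-week recall | none stated |
| Patient-Specific Functional Scale | MPK evaluation point | none stated |
| Mailer falls | bi-weekly | yes, up to the stop |

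**3. Size of the distortion.** Inputs, all assumed because the documents give none: stopping share p = 5%, 10% or 20%; stayers' gain 0.40 SD of the within-subject difference (close to the 0.40 detectable in step 1); stoppers' effect s = 0 or −0.40.

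All-fitted effect = 0.40 × (1 − p) + s × p. Overstatement = 0.40 / (all-fitted effect) − 1.

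| p | s = 0: effect | overstated by | s = −0.40: effect | overstated by |
|---|---|---|---|---|
| 5% | 0.38 | 5% | 0.36 | 11% |
| 10% | 0.36 | 11% | 0.32 | 25% |
| 20% | 0.32 | 25% | 0.24 | 67% |

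**4. False-positive risk.** Suppose the mean effect in all fitted subjects is zero and stoppers lose L. Stayers then average L × p / (1 − p), tested by a paired t-test on 50 × (1 − p) pairs. Rejection in favour of the MPK (noncentral t), against a nominal 2.5%:

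| L | p = 10% (45 pairs) | p = 20% (40 pairs) |
|---|---|---|
| 0.80 | stayers' mean 0.089; 8.4% | stayers' mean 0.20; 23.4% |
| 0.40 | stayers' mean 0.044; 4.8% | stayers' mean 0.10; 9.0% |

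The upper row is a severe case. The lower row shows how quickly the result moves with the assumed loss.

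**The case against.** *Falls are already covered.* A reader might infer that all MPK outcomes are collected only after acclimation, so that the fall-rate hypothesis (Hypothesis 2) is lost as well. The documents contradict this: the mailers cover the earlier weeks, and an early stopper can supply MPK falls. The plan does not say how partial exposure would be counted, and the PEQ-A items remain exposed, but the main falls comparison is not in the same position.

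*The text does not forbid an early packet.* A rotation cut short also has an end, and all materials go by mail. A reader might infer a rule that early stoppers are never measured, or a stated complete-case analysis. Neither is written. What stands is that staff have no instruction, and that exclusion follows from the default behaviour of the named tests.

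*Acclimated performance is a legitimate target.* The plan ties the period to practice in similar studies. An early value mixes learning-phase with acclimated performance, and the four-week recall may include NMPK use. This stands, and it is the reason not to make the early value the main B value.

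*Rate, reasons and direction are assumed.* Some stops may reflect illness, relocation or unreturned mail. The entry criteria also require a well-fitting socket and no current stump problems. This stands too: the bias favours the MPK only if stoppers do worse than stayers.

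*A likelihood-based model can use A1.* It can, through the correlation between A1 and B, and this helps if stopping depends on baseline function. It does not help where stopping depends on how the subject fares on the MPK.

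**Conclusion.** The point holds for activity, SF-36, PEQ, PEQ-A and the Patient-Specific Functional Scale: the plan schedules no MPK measurement for a subject who stops before the post-acclimation test. It does not hold for mailer falls. Under the assumed 5 to 20% stopping and a stayers' gain of 0.40 SD, the overstatement is 5 to 25% if stoppers gain nothing and 11 to 67% if they lose 0.40 SD. These figures illustrate sensitivity; they do not estimate what will happen. A reader might infer that the trial is bound to be biased towards the MPK, but the documents give neither a stopping rate nor reasons, so neither the size nor the direction can be established from them. The change is still worth making, because it is cheap and the data cannot be recovered afterwards.

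**What to change.** 1. In Study Design, Methods and in Patient Satisfaction and Safety, state that when the MPK is stopped before the planned test, staff mail the B questionnaires (SF-36, PEQ, PEQ-A, Patient-Specific Functional Scale) at once, with the activity monitors if the MPK is still worn. No knee change is delayed for this. Record the stop date and the reason.
2. In the Data Analysis Plan, keep the acclimated comparison as planned and add an all-fitted sensitivity analysis that uses the early-stop B values.
3. Report the number who stopped, their reasons and their mailer falls while on the MPK as a safety result.

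Cost: a short protocol addition, one mailed packet per stopper and one extra analysis. Downside: early-stop values reflect shorter acclimation and may partly recall NMPK use, so the sensitivity estimate may be less favourable to the MPK. It should be read beside the acclimated estimate and not as its replacement.

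### The plan names no deciding MPK versus NMPK comparison across its A-B-A periods, and its global test also responds to change over time

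*Combined protocol and SAP*

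**What the plan says.** Study Design, Methods, fixes one order for every subject: "Each subject will be tested using their current NMPK, fit and tested with a MPK, and then tested again with their NMPK". The same section confirms three evaluations: "Subjects will also fill out the Patient-Specific Functional Scale at each of the 3 evaluation points". It describes an acclimation period, typically about 4 months, "before testing is commenced on the MPK". It states no interval between the return to the NMPK and the second NMPK evaluation. The satisfaction and safety text asks about the preceding four weeks at the close of each rotation.

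Statistical Information, Power Statement, treats the study as a single paired comparison of two devices: "80% power to detect differences in means between the two devices (MPK vs. NMPK) of at least 0.56 standard deviations".

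The Data Analysis Plan gives the device question to a global test: "The effects of these two prosthesis designs on these outcome variables will be evaluated using a one-factor repeated measures ANOVA", with Friedman's test as the non-parametric alternative. It then adds, for either global test: "Comparisons of A1 versus B, and A2 versus B will be also conducted using multiple comparison procedures or contrasts following the global ANOVA". The levels of the factor are not listed. For falls, the subject of Hypothesis 2, it says: "The information about falls from the biweekly fall tracking mailers will be compiled and compared across prosthesis type (MPK vs. NMPK"). It does not say whether NMPK there means A1, A2 or both.

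**The concern.** A global test followed by A1 versus B and A2 versus B presupposes a factor with levels A1, B and A2. The null hypothesis of that test is that all three means are equal. It is false whenever the same NMPK scores differently on the two occasions, whatever the MPK does. So it tests for any change across three visits in a fixed order, and is not specific to the device.

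The two follow-ups are device comparisons, and a linear drift pushes them in opposite directions, which is useful. What is missing is a rule. Nothing says whether the global test, A1 versus B, A2 versus B or some combination decides Hypothesis 1a, or how A1 and A2 become the one NMPK value that the power statement assumes. Nothing says what is concluded if one follow-up is significant and the other is not, or if their signs differ. The device conclusion can then rest on a choice made after the data are seen. Because the order is not randomised, change over time is the natural rival explanation.

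**Working it through.** **Inputs.** From the documents: 50 subjects, paired design, 80% power, 0.56 SD, three evaluations in the order A1, B, A2. Not given, so assumed: two-sided 5%, unit SD at each evaluation, equal correlation rho between evaluations (0 to 0.7), and the drift and carry-over sizes. Means are written (A1, B, A2).

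**1. The plan's own figure.** 0.56/sqrt(2/50) = 0.56/0.2 = 2.80, and Phi(2.80 - 1.96) = 80.0%. So 0.56 reproduces as a difference between two means in SDs of a single score with rho = 0 (paired noncentral t: 78.4%). Read as SDs of the paired difference, power would be 97.3%. Either way it is one two-device difference, with no weights for A1 and A2.

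**2. Global test under drift, no device effect.** Means (0, 0.2, 0.4) have average 0.2 and squared deviations summing to 0.04 + 0 + 0.04 = 0.08. The noncentrality is lambda = 50 x 0.08/(1 - rho) = 4.0/(1 - rho), with 2 and 98 df.

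| rho | lambda | Global ANOVA rejects | B-(A1+A2)/2 rejects |
|---|---|---|---|
| 0 | 4.00 | 40.4% | 5% |
| 0.3 | 5.71 | 54.8% | 5% |
| 0.5 | 8.00 | 70.3% | 5% |

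The contrast stays at 5% because 0.2 - (0 + 0.4)/2 = 0. For rho 0 to 0.5, Friedman's test rejects in 30% to 54% (simulation). With drift of 0.1 SD per period the global ANOVA rejects in 13% to 22%.

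**3. Global test plus at least one significant follow-up.** This is one possible reading of the plan. With Bonferroni follow-ups, same drift and rho 0 to 0.5, simulation gives about 19% to 38% (the ends move by about one point depending on whether the follow-ups use paired t-tests or the ANOVA error term).

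**4. Power at a true 0.56 SD, no drift.** Means (0, 0.56, 0).
- Global, rho 0: lambda = 50 x 0.56^2 x 2/3 = 10.45, power 82%.
- Contrast variance: 1 + (1 + rho)/2 - 2 rho = 1.5(1 - rho). At rho 0, 0.56/sqrt(1.5/50) = 3.23, power 88.7%. At rho 0.3 and 0.5: 96.6% and 99.4%.

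**5. How often the follow-ups split.** True 0.56 SD, each follow-up at an unadjusted 5%, exactly one significant (simulation):

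| rho | No drift | Drift 0.2 SD per period |
|---|---|---|
| 0 | 24% | 54% |
| 0.3 | 13% | 44% |
| 0.5 | 4% | 29% |
| 0.7 | under 1% | 10% |

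**6. Falls.** Assumed rates 1, g, g^2 per unit of person-time, no device effect. With g = 0.9, B/A1 = 0.90 and B/A2 = 0.9/0.81 = 1.11. With g = 0.8 they are 0.80 and 0.8/0.64 = 1.25. On the log scale, ln g - (0 + 2 ln g)/2 = 0, a ratio of 1.00. So the choice of NMPK period can set the direction of the result.

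**7. Limits of the contrast** (with both follow-ups pointing the same way; rho 0 to 0.7; simulation).
- Unequal spacing, assumed (0, 0.2, 0.25), no device effect: the contrast is 0.2 - 0.125 = 0.075, and it rejects in about 7% to 11%.
- Plateau or learning, (0, 0.3, 0.3), no device effect: the contrast is 0.15, and it rejects in about 14% to 31%. Requiring both follow-ups to be significant in the same direction gives 2.0% to 2.5%.
- True effect 0.56 SD, half carried into A2, (0, 0.56, 0.28): power is about 66% to 99% for the contrast rule and 26% to 70% for the both-significant rule.

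**The case against.** The strongest reply is that the plan already contains the device comparisons. A1 versus B and A2 versus B are named, a multiple comparison procedure is allowed, and the reversal exists to expose change over time. That much stands. A reader might infer from the 40% to 70% figures that the plan would declare a false device effect that often. The documents do not support this: nothing says that a significant global test alone carries the device claim, so these are properties of that test and not the plan's false-claim rate. Naming two comparisons without a rule still leaves the verdict open when they differ.

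Second, the three levels are inferred. If the factor had only two levels, the drift argument would not apply in this form. But the plan would then need a rule for merging A1 and A2, and it has none.

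Third, a reader might infer that A2 is contaminated by carry-over because no acclimation is described before it. The four-week recall at the end of each rotation implies at least four weeks back on the NMPK. Carry-over is neither shown nor excluded.

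Fourth, it is tempting to prefer the both-significant rule as protection against carry-over. Carry-over of an MPK effect presupposes such an effect, so failing to reject then is lost power and not error control. That rule helps only against a plateau or learning effect.

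**Conclusion.** The gap is real and should be closed before analysis. The plan gives the device question to a test that is not specific to the device, and supplies neither a deciding comparison nor a rule for combining A1 and A2 or for split results. That conclusion needs no assumed magnitude. The size does: drift, correlation, alpha and sidedness are not in the documents. At the assumed 0.2 SD per period the global test is badly inflated while the contrast holds 5%, and without drift the contrast also has more power. Split follow-ups are common at low correlation or with drift, and rare at high correlation without drift.

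The contrast is better but not a cure. Its protection against linear drift needs A1 to B and B to A2 to be about equally spaced, and the documents give about 4 months before MPK testing and no interval to A2. Neither an actual drift nor a wrong device conclusion can be inferred from the text.

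**What to change.** Before analysis, write into the Data Analysis Plan:

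- The device test for each outcome is the one-degree-of-freedom contrast B-(A1+A2)/2 at two-sided 5%. A device claim also requires A1 versus B and A2 versus B to point the same way.
- Report A1 versus B, A2 versus B and A1 versus A2 with confidence intervals. Keep the global ANOVA or Friedman's test as descriptive.
- For clearly non-Gaussian outcomes, use a signed-rank test on the same per-subject contrast.
- For falls, model the rate per person-time in each period and test log rate B minus the mean of log rates A1 and A2.
- State the limits: the equal-spacing condition (report the actual intervals), no protection against a plateau or learning effect, and lower power if an MPK effect carries into A2.
- Optionally report, as a stricter sensitivity check against a plateau or learning effect, whether both follow-ups are significant in the same direction. Do not present it as a remedy for carry-over.

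The cost is SAP wording and minor programming, with no added subjects or visits. Power does not suffer relative to the global test in the no-drift case. A subject without all three evaluations gives no per-subject contrast, so report how many lack each one. A mixed model with occasion as a fixed factor can estimate the same contrast from all available evaluations as a secondary analysis.
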